2.1. Overview of NASH and Role of VAP-1/SSAO in Disease

Terns is developing TERN-201, an investigational, potent, and highly selective, irreversible covalent inhibitor of human vascular adhesion protein-1(VAP-1)/semicarbazide-sensitive amine oxidase for the treatment of patients with non-alcoholic steatohepatitis (NASH).

NASH is an advanced form of non-alcoholic fatty liver disease (NAFLD), the most common cause of chronic liver disease in North America ([Chalasani 2018](#)). NASH is characterized by the presence of hepatic inflammation and hepatocellular ballooning, with or without fibrosis. NASH is a progressive condition that can lead to cirrhosis, decompensated liver disease, and increased risk for hepatic carcinoma and liver-related mortality ([Ekstedt 2015](#)). Currently, there are no approved therapies for the treatment of NASH. With an aging population and the emergence of overlapping epidemics of obesity, diabetes, and dyslipidemia/metabolic syndrome, NAFLD and NASH have increased greatly in prevalence ([Andronescu 2018](#)), posing a significant healthcare challenge.

VAP-1/SSAO is a cellular adhesion protein and ectoenzyme expressed on the vascular endothelium that has long been recognized as a mediator of leukocyte adhesion and extravasation in the setting of inflammation ([Salmi 2019](#)). The enzymatic activity of VAP-1 further contributes to inflammation and oxidative stress by converting primary amines to aldehyde, ammonia, and hydrogen peroxide. VAP-1 levels are increased in the liver tissue and blood of patients with NASH and circulating VAP-1, termed soluble VAP-1 (sVAP-1), is independently associated with fibrosis stage ([Weston 2015](#)). Genetic and pharmacology studies indicate VAP-1 deficiency or inhibition attenuate steatosis, inflammation, and fibrosis in NASH models. VAP-1 deficiency attenuates carbon tetrachloride (CCl₄)-induced hepatic fibrosis and VAP-1 knockout mice exhibit reduced hepatic steatosis and fibrosis when fed a western lifestyle diet. Moreover, treatment with a VAP-1 antibody reduces inflammation, steatosis, and fibrosis in a methionine choline-deficient diet mouse model of NASH ([Weston 2015](#)).

Based on these observations, VAP-1 inhibition is anticipated to reduce inflammation and fibrosis in NASH patients. This novel mechanism provides a potential opportunity to treat NASH, a disease with significant unmet medical needs.

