5.2. Exclusion Criteria

Patients are excluded from the study if any of the following criteria apply at Screening:

Medical Conditions

1. History or clinical evidence of chronic liver diseases other than NAFLD or NASH including but not limited to:
 - Active hepatitis B virus (HBV) infection defined as positive HBV surface antigen at screening
 - Active hepatitis C virus (HCV) infection defined as positive HCV antibody (anti-HCV) and HCV ribonucleic acid (RNA). Patients with anti-HCV but negative HCV RNA will be eligible for participation if HCV RNA has been negative for at least 1 year.
 - Autoimmune liver disease
 - Primary biliary cirrhosis
 - Primary sclerosing cholangitis
 - Wilson's disease (history should include normal serum ceruloplasmin and 24-hour urinary copper)
 - Gilbert's syndrome
 - Hemochromatosis or other iron overload
 - Alpha-1-antitrypsin (AAT) deficiency (history should include normal AAT genotype and serum AAT level)
 - Alcoholic liver disease
 - Prior known drug-induced hepatotoxicity
 - Known bile duct obstruction
 - Suspected or proven liver cancer
2. History or clinical evidence of cirrhosis, hepatic decompensation, or other severe liver impairment, including ascites, hepatic encephalopathy, and variceal bleeding
3. History of liver transplant, or current placement on a liver transplant list
4. ALT or AST $> 5 \times$ upper limit of normal (ULN)
5. Unstable elevated ALT or AST. Patients with ALT or AST > 60 IU/L must have evidence of a stable ALT and AST over at least a 2-week time period prior to randomization as evidenced by one of the following:

- Comparison to prior ALT and AST (historical values) obtained within 2-12 weeks prior to the Screening visit: Screening ALT and AST values should be $\leq 30\%$ higher than a documented prior result, OR
- Repeat ALT and AST values at least 2 weeks after the Screening visit: Repeat ALT and AST should be $\leq 30\%$ higher than the values from the Screening visit, and the repeat values must be $\leq 5 \times \text{ULN}$
- If the Investigator has clinical suspicion for acute liver injury in a patient for other reasons, the patient should be excluded after discussion with the Medical Monitor.
- The MRI cT1 may proceed on the basis of the initial ALT and AST values at Screening, given all other eligibility criteria are met, but randomization should not occur prior to confirmation of ALT and AST stability, as necessary.

6. Total bilirubin $> 1.2 \text{ mg/dL}$

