7.1. Discontinuation of Study Drug

Study drug must be discontinued for an individual patient in the following instances:

- If an AE of Grade 3 or above (National Cancer Institute (NCI) CTCAE 5.0) occurs and is considered related to study drug as judged by the Investigator per the guidance in [Appendix 6](#)
- Symptoms of COVID-19 requiring hospitalization
- Change in clinical status that, in the judgement of the Investigator compromises the patient's ability to continue treatment or is not considered to be in the patient's best interest
- Patient request to discontinue study drug for any reason
- Pregnancy during the study (refer to [Appendix 7](#))
- Sponsor discretion
- Discontinuation of the study at the request of the Sponsor, a regulatory agency, or Institutional Review Board (IRB)/Independent Ethics Committee (IEC)

Resumption of study drug may be considered in discussion with the Medical Monitor and Sponsor.

If one of the following situations occurs and is considered related to the study drug without alternative etiology, study drug may be discontinued at the discretion of the Investigator and the Medical Monitor should be informed (with repeat test performed within 48-72 hours once initial abnormality is detected):

- ALT or AST $> 8 \times$ ULN
- ALT or AST $> 5 \times$ ULN for more than 1 week, confirmed with a repeat assessment
- ALT or AST $> 2 \times$ Baseline with the appearance of fatigue, nausea, vomiting, right upper quadrant pain or tenderness, fever, rash, and/or eosinophilia $> 5\%$
- ALT or AST $> 2 \times$ Baseline and total bilirubin $> 2 \times$ ULN or INR > 1.5 for more than 1 week, confirmed with a repeat assessment

In addition, Investigators may permanently discontinue study drug at their discretion due to patient non-compliance with study drug or study assessments.

If study drug is permanently discontinued, the patient will remain in the study to be evaluated during the Follow-Up Period. See the Schedule of Activities for data to be collected at the time of discontinuation of study drug and follow-up and for any further evaluations that need to be completed.

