8.1.8. Transient Elastography and Controlled Attenuation Parameter

Liver stiffness will be assessed by vibration-controlled transient elastography (via FibroScan[®]) at Screening to determine study eligibility. If results from transient elastography measurement within 3 months of Screening are available, these values can be used to assess eligibility and do not need to be repeated.

The transient elastography requirement is intended to select for patients likely to have at least F1 fibrosis. The protocol excludes patients with cirrhosis based on medical history or clinical signs or symptoms (Exclusion criteria #2). Prior studies indicate variability in the ranges of liver stiffness measured by transient elastography in NASH patients with fibrosis or cirrhosis. In STELLAR-3, which enrolled patients with bridging fibrosis, median liver stiffness at baseline was approximately 13 kPa, with an interquartile range between 10 and 17 kPa ([Harrison 2020](#)). In STELLAR-4, which enrolled patients with cirrhosis, median liver stiffness at baseline was approximately 20-21 kPa, with an interquartile range between 14 and 30 kPa ([Harrison 2020](#)). The utility of transient elastography to diagnose cirrhosis in the setting of NASH also appears limited based on the low positive predictive value (PPV) of even relatively high kPa thresholds. For a threshold of 21 kPa, the upper limit for this study, the PPV for F4 fibrosis (i.e., cirrhosis) in the setting of NASH is 0.37 (which may be even lower in a population with low prevalence of

cirrhosis, such as one in which cirrhosis is excluded on clinical grounds), with a negative predictive value of 0.96 ([Eddowes 2019](#)). This threshold has a sensitivity of 0.59 and a specificity of 0.90 for a diagnosis of cirrhosis in the setting of NASH ([Eddowes 2019](#)).

CAP is an assessment of liver steatosis and is generally used to complement the assessment of liver stiffness by transient elastography for evidence of NASH ([Eddowes 2019](#)). CAP estimates the total ultrasonic attenuation (go-and-return path), expressed in dB/m, based on the postulate that fat affects ultrasound propagation. A CAP threshold of 274 dB/m has sensitivity of 0.9 and specificity of 0.6 for identification of liver steatosis of $\geq 5\%$ ([Eddowes 2019](#)). The threshold of 280 dB/m was chosen to identify patients who are likely to have elevated liver steatosis, in conjunction with the other imaging assessments at screening, including cT1.

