Appendix 4: Fridericia's Formula

A single 12-lead ECG will be obtained as outlined in the Schedule of Activities (see [Section 1.3](#)) using an ECG machine that automatically calculates the heart rate and measures PR, QRS, and QT intervals. QTc will be calculated using Fridericia's Formula as outlined below.

The Investigator will review the ECGs for any clinically significant abnormalities.

Fridericia's Formula:

$$QTcF = QT / (RR^{0.33})$$

<http://www.thecalculator.co/health/QTc-Calculator-385.html>

Appendix 5: Chronic Kidney Disease Epidemiology Collaboration (CKD-EPI) Formula to Estimate Glomerular Filtration Rate

$$\text{GFR} = 141 \times \min(S_{\text{Cr}}/\kappa, 1)^\alpha \times \max(S_{\text{Cr}}/\kappa, 1)^{-1.209} \times 0.993^{\text{Age}} \times 1.018 \text{ [if female]} \times 1.159 \text{ [if black]}$$

Abbreviations / Units:

SCr (standardized serum creatinine) = mg/dL

κ = 0.7 (females) or 0.9 (males)

α = -0.329 (females) or -0.411 (males)

min = indicates the minimum of SCr/ κ or 1

max = indicates the maximum of SCr/ κ or 1

age = years

Appendix 6: Adverse Events: Definitions and Procedures for Recording, Evaluating, Follow-up, and Reporting

AE Definition

- An AE is any untoward medical occurrence in a patient or clinical study patient, temporally associated with the use of study drug, whether or not considered related to the study drug.
- NOTE: An AE can therefore be any unfavorable and unintended sign (including an abnormal laboratory finding), symptom, or disease (new or exacerbated) temporally associated with the use of study drug.

Events Meeting the AE Definition

- Any safety assessment (e.g., ECG, radiological scans, vital signs measurements), including those that worsen from baseline, considered clinically significant in the medical and scientific judgment of the Investigator (i.e., not related to progression of underlying disease).
- A clinical condition or symptom associated with an abnormal laboratory test result (e.g., hematology, clinical chemistry, or urinalysis). An abnormal laboratory test that is not accompanied with other signs or symptoms should not be reported as an AE.
- Exacerbation of a chronic or intermittent pre-existing condition including either an increase in frequency and/or severity of the condition.
- New conditions detected or diagnosed after study drug administration even though it may have been present before the start of the study.

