- Signs, symptoms, or the clinical sequelae of a suspected drug-drug interaction.
- Signs, symptoms, or the clinical sequelae of a suspected overdose of either study drug or a concomitant medication. Overdose per se will not be reported as an AE/SAE unless it is an intentional overdose taken with possible suicidal/self-harming intent. Such overdoses should be reported regardless of sequelae.

Events NOT Meeting the AE Definition

- Abnormal laboratory findings or other abnormal safety assessments that are associated with an underlying disease present at baseline without worsening, unless judged by the Investigator to be more severe than expected for the patient's condition.
- An abnormal laboratory test that is not accompanied with other signs or symptoms.
- The disease/disorder being studied or signs, or symptoms of the disease/disorder being studied, unless more severe than expected for the patient's condition.
- Medical or surgical procedure (e.g., endoscopy, appendectomy): the condition that leads to the procedure is the AE.
- Situations in which an untoward medical occurrence did not occur (social and/or convenience admission to a hospital).
- Anticipated day-to-day fluctuations of pre-existing disease(s) or condition(s) present or detected at the start of the study that do not worsen.

Definition of SAE

An SAE is an AE that meets the following criteria:

An SAE is defined as any untoward medical occurrence that, at any dose:

a. Results in death

b. Is life-threatening

The term 'life-threatening' in the definition of 'serious' refers to an event in which the patient was at risk of death at the time of the event. It does not refer to an event, which hypothetically might have caused death, if it were more severe.

c. Requires inpatient hospitalization or prolongation of existing hospitalization

- In general, hospitalization signifies that the patient has been detained (usually involving at least an overnight stay) at the hospital or emergency ward for observation and/or treatment that would not have been appropriate in the physician's office or outpatient setting. Complications that occur during hospitalization are AEs. If a complication prolongs hospitalization or fulfills any other serious criteria, the event is serious. When in doubt as to whether "hospitalization" occurred or was necessary, the AE should be considered serious.

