- Hospitalization for elective treatment of a pre-existing condition that did not worsen from baseline is not considered an AE.

d. Results in persistent disability/incapacity

- The term disability means a substantial disruption of a person's ability to conduct normal life functions.
- This definition is not intended to include experiences of relatively minor medical significance such as uncomplicated headache, nausea, vomiting, diarrhea, influenza, and accidental trauma (e.g., sprained ankle) which may interfere with or prevent everyday life functions but do not constitute a substantial disruption.

e. Is a congenital anomaly/birth defect

f. Other situations:

- Medical or scientific judgment should be exercised in deciding whether SAE reporting is appropriate in other situations such as important medical events that may not be immediately life-threatening or result in death or hospitalization but may jeopardize the patient or may require medical or surgical intervention to prevent one of the other outcomes listed in the above definition. These events should usually be considered serious.
- Examples of such events include invasive or malignant cancers, intensive treatment in an emergency room or at home for allergic bronchospasm, blood dyscrasias or convulsions that do not result in hospitalization, or development of drug dependency or drug abuse.

If an event does not meet the AE definition, then it cannot be an SAE even if serious conditions are met (e.g., hospitalization for signs/symptoms of the disease under study, death due to progression of disease).

Recording and Follow-Up of an AE and/or SAE

AE and SAE Recording

- When an AE and/or SAE occurs, it is the responsibility of the Investigator to review all documentation (e.g., hospital progress notes, laboratory reports, and diagnostics reports) related to the event.
- The Investigator will then record all relevant AE and/or SAE information in the eCRF.
- It is **not** acceptable for the Investigator to send photocopies of the patient's medical records to the Sponsor or designee in lieu of completion of the AE or SAE eCRF.
- There may be instances when copies of medical records for certain cases are requested by the Sponsor or designee. In this case, all patient identifiers, with the exception of the patient number, will be redacted on the copies of the medical records before submission to the Sponsor or designee.

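### Protocol Appendix 6 lets a clinical liver event go unrecorded if the investigator judges it to be NASH and no more severe than expected

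*Protocol*

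**What the plan says.** All the definitions are in Protocol Appendix 6. Section 8.5 of the protocol refers to that appendix for which events qualify.

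- **Not an AE:** "The disease/disorder being studied or signs, or symptoms of the disease/disorder being studied, unless more severe than expected" for the patient's condition.
- **Not an SAE:** an event that fails the AE definition cannot be serious, "even if serious conditions are met (e.g., hospitalization for signs/symptoms of the disease under study, death due to progression of disease".
- **Safety assessments:** a worsened finding counts as an AE if "considered clinically significant in the medical and scientific judgment of the Investigator (i.e., not related to progression of underlying disease".
- **In the other direction:** the list of qualifying events includes "Exacerbation of a chronic or intermittent pre-existing condition including either an increase in frequency and/or severity of the condition". It also includes conditions first detected after dosing, even if they may have been present before the study.

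Protocol Section 8.5.1 collects all AEs and SAEs from first dose through follow-up regardless of cause, and requires SAEs to be reported within 24 hours. Protocol Section 9.4.2 promises a summary of deaths.

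**The concern.** Treatment-emergent AEs are part of the primary endpoint, and the liver is both the diseased organ and one in which drug harm may show. A drug-related liver event and a NASH event can look alike. The usual safeguard is to record the event and then rate its cause. Here the disease judgment comes first. If the investigator decides that the event is NASH and no worse than expected, there is no AE record on which to rate causality.

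Such an event would miss:

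- the 24-hour SAE report (Protocol Section 8.5.1);
- the causality rating (Appendix 6), whose *Possibly Related* category is meant for events that the patient's clinical state could also explain;
- the treatment-emergent, serious and fatal outputs (SAP Sections 9.2, 9.2.1 and 9.2.2). The death row and the death listing are both drawn from AE records, so neither would show a death classed as non-AE progression, despite the summary promised in Protocol Section 9.4.2.

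The treatment-related outputs, and the mandatory stop for a related AE of Grade 3 or above (Protocol Section 7.1), are lost only if the investigator would have rated the event *Possibly Related* or *Related*.

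**Working it through.** No arithmetic applies, because the documents state no figure on this point. The check sets the texts side by side.

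1. **The collection rule does not help.** Section 8.5.1 collects events whatever their cause, but only events that already meet the Appendix 6 definition.

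2. **The disease bullet differs from its neighbours.** Of the other exclusions, the one for abnormal findings tied to baseline disease applies only where there is no worsening. The one for day-to-day fluctuation applies only to conditions that do not worsen. The disease-under-study bullet has no such limit, only the exception for greater than expected severity. Read literally, NASH that worsens as expected is excluded.

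3. **The SAE sentence reinforces this.** It begins by assuming that the event has failed the AE definition, so the severity condition carries over. But progression is worsening. Giving death from progression as an example implies that a worsening of the study disease, even a fatal one, can fall outside the AE definition.

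4. **The exacerbation bullet says the opposite.** An increase in severity of a pre-existing condition is an AE, and the general definition also covers exacerbated disease. No rule says which prevails.

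5. **Whether an event is expected is open to argument.** Protocol Section 2.1 says that "NASH is a progressive condition that can lead to cirrhosis, decompensated liver disease, and increased risk for hepatic carcinoma and liver-related mortality". Section 5.1 admits biopsy stages F1 to F3, and Section 8.1.9 links high cT1 values to encephalopathy, variceal bleeding, ascites and death. Against that, Exclusion 2 bars "History or clinical evidence of cirrhosis, hepatic decompensation, or other severe liver impairment, including ascites, hepatic encephalopathy, and variceal bleeding", which makes decompensation on study hard to call expected. Two investigators could still differ over a lesser clinical worsening.

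| Event judged to be NASH | Disease bullet | Exacerbation or new-condition bullet |
|---|---|---|
| Stable symptoms | Not an AE | Not triggered |
| Clinical worsening, judged expected | Not an AE | AE |
| Worse than expected | AE | AE |
| Cirrhosis first detected on study | Depends on the judgment | AE (new condition) |

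The direct conflict is in the second row. The fourth conflicts only if the investigator calls the finding expected.

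6. **What is captured anyway.** These routes do not need an AE record: laboratory grading, shifts and Hy's-rule listings (SAP Sections 9.3.1 to 9.3.3), discontinuation reasons (SAP Section 7.1), and the mandatory stop for "Change in clinical status that, in the judgement of the Investigator compromises" continued treatment (Protocol Section 7.1). For an on-study death, Appendix 6 requires a copy of any post-mortem findings, but that provision sets no time limit for notifying the death itself.

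**The case against.** The strongest reply is that Appendix 6, read as a whole, already captures these events. The SAE examples illustrate events that have failed the AE test, so they need not repeat the severity condition. The neighbouring bullets exclude only what does not worsen, which suggests that worsening NASH was meant to be reportable. Complications arising during a hospitalization are stated to be AEs. Patients enter without cirrhosis or decompensation and within limits for bilirubin, albumin, INR and platelets, so a serious liver event would ordinarily exceed expectation. Most of this stands, and it is why the point is minor. It does not settle the conflict in the second row of the table, and the examples push a site towards not reporting.

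Three stronger readings are tempting, but the documents do not support them.

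- *All hospitalizations and deaths from NASH are exempt.* The opening clause of the SAE sentence rules this out.
- *The gap can be sized from unrecognized cirrhosis below 21 kPa.* Protocol Section 8.1.8 gives a negative predictive value of 0.96 and says: "This threshold has a sensitivity of 0.59 and a specificity of 0.90 for a diagnosis of cirrhosis in the setting of NASH". A reader might infer that 1 − 0.96 = 4% of patients are at risk, as an upper figure. But the 6.5 kPa floor in Inclusion 4 raises that share while the clinical exclusions lower it, so 4% is not a bound. Patients who enter by biopsy are outside the calculation. It would also size a subgroup whose newly found cirrhosis is already an AE, not the number of unrecorded events.
- *Vital-sign findings are lost because they are not in the database.* SAP Section 9.4 reports clinically significant abnormalities as AEs, with no disease exception.

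**Conclusion.** The point holds as a minor one. Appendix 6 contains two rules that disagree about expected worsening of NASH, and one of them lets the investigator screen a clinical liver event out before causality is rated. The number of events affected is unknown, and the documents give no basis for estimating it. Few are expected, given non-cirrhotic patients, 12 weeks of treatment and 4 weeks of follow-up, and the other text that captures serious events. The reason to act is that the change is cheap and that a missed event would bear on the primary safety endpoint. This conclusion assumes that no site instruction outside the documents already resolves the conflict.

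**What to change.** Two edits to Protocol Appendix 6:

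1. Delete the parenthetical examples from the sentence on events that cannot be SAEs.
2. Replace the disease-under-study bullet with:

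> NASH as present at baseline, and its signs or symptoms without clinical worsening. Every death, every non-elective hospitalization meeting SAE criteria, and every clinical worsening or decompensation of liver disease (ascites, hepatic encephalopathy, variceal bleeding) after first dose is recorded as an AE, and as an SAE if serious, whatever the presumed cause.

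Attribution to NASH is then recorded on the existing four-category causality scale, where *Not Related* already covers the patient's clinical state.

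The progression qualifier on safety assessments should not simply be deleted. That bullet covers radiological scans, and without the qualifier a worsening cT1 or PDFF result, which is an exploratory efficacy measure, could become an AE. Keep it for protocol-scheduled efficacy imaging (MRI cT1/PDFF and elastography), or limit any deletion to other safety assessments. The elective-admission exemption and the rule on isolated laboratory abnormalities stay as they are.

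The cost is a wording change, a site instruction and possibly a few more AE and SAE reports. The SAP outputs do not change.
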